5.3.2 Exclusion criteria

1. Symptomatic SARS-CoV-2 infection at any stage prior to the baseline visit **[Cohort 1 only]**.
2. SARS-CoV-2 infection, confirmed through a documented positive PCR, antigen, or antibody test, prior to vaccination in a non-placebo arm of a COVID-19 vaccine study during 2020 **[Cohort 4 only]**.
3. COVID-19 within three months of the baseline visit.
4. Personnel (e.g., investigator, sub-investigator, research assistant, pharmacist, study coordinator or anyone mentioned in the delegation log) directly involved in the conduct of the study.
5. Any physical, mental, or social condition, that, in the Investigator's judgment, might interfere with the completion of the baseline assessments and evaluations. The Investigator should make this determination in consideration of the volunteer's medical history.

6. Participant is judged by the Investigator to be at significant risk of failing to comply with the provisions of the protocol as to cause harm to self or seriously interfere with the validity of the study results.

5.4 Sub-Study Eligibility Criteria (Subsequent Optional Visit(s))

The following additional eligibility criteria will be used to identify study participants who are eligible for random selection for any of the sub-studies. Participants may be enrolled into more than one sub-study.

5.4.1 Inclusion criteria

1. Enrolled into main study and completed baseline visit.
2. Willing to provide written or electronic information consent for the relevant sub-study.

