- 2 Written or electronic informed consent to be provide prior to any screening or study-specific assessments, questionnaires or procedures are conducted.
- 3 Including dates of diagnosis through SARS-CoV-2 PCR or antigen testing, or date of positive antibody testing, COVID-19 vaccination dates (if administered), COVID-19 hospitalisation dates (if applicable).
- 4 Including information related to specific risk factors associated with poor COVID-19 outcomes and a detailed history of previous COVID-19 episodes (if applicable).
- 5 Targeting symptoms not covered in other administered surveys and questionnaires.
- 6 Details regarding previous and concomitant medications from the time of the participant's confirmed SARS-CoV-2 infection will be collected.
- 7 Including height and weight, and at least a general, cardiorespiratory, and skin examination and other systems as indicated through reported symptoms.
- 8 Vital signs (blood pressure, pulse rate, respiratory rate, body temperature, and SpO₂) will be measured after 5 min resting.
- 9 A standard 12-lead ECG will be conducted after the participant has rested in the supine position for 10 minutes.
- 10 A blood sample will be collected for full blood count, serum chemistry, liver function, renal function, glucose, HbA1C, and inflammatory markers assessments, and for DNA extraction for genotyping and sequencing.
- 11 Blood (50 mL) and urine (100 mL) samples will be stored for possible future analysis pending emerging information.
- 12 Study team personnel will review each participant's baseline data and identify participants with and without Long-COVID who are eligible for participation in one, or more, sub-study. Invited participants will be randomly selected from the set of eligible participants for each sub-study. Participants who decline the invitation to participate in one, or more, sub-study, will be replaced by a randomly selected, matched-cohort participant where possible.
- 13 Participants will be contact telephonically to inform them of the results of their baseline assessments, and to arrange for follow-up clinical consultations as required for any identified medical or mental health issues. Participants that have been selected for sub-study participation will be invited to return for consent and enrolment into these sub-studies.

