5.3 Main Study Eligibility Criteria (Baseline Visit)

The following eligibility criteria will be used to select study participants for the main study (baseline visit only).

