6. STUDY VISITS

A brief screening assessment will be conducted for all study participants who provide informed consent for participation in the study. Those who are eligible for enrolment will continue into a baseline visit where all main study questionnaires will be administered, and assessments and procedures conducted.

Participants who are eligible for various sub-studies will be identified by the study team after review of their baseline visit results. Sub-study participants (up to 30 per cohort per sub-study) will be selected from these eligible participants and will be invited to provide separate informed consent for each sub-study. An additional visit or visits will be conducted for each sub-study. The number of study visits for each participant will depend on the number and type of sub-studies in which they participate. All study visits (including the screening/baseline visits and sub-study visits) will be completed for each participant within approximately 6 months.

Participants will be contacted telephonically within 28 days of the baseline visit, and again within 28 days of their last sub-study visit (if relevant) to inform them of the results of their assessments. For participants taking part in the overnight sleep study, however, feedback may be delayed until 6 months from the overnight visit. Abnormalities detected in assessments (suggesting undiagnosed medical, mental health, or sleep issues) will be managed by on-study medical personnel with referral as appropriate.

Questionnaires to be administered, and assessments and procedures to be conducted at each study visit (main and sub-studies) are detailed in Section 1. Details regarding each questionnaire, assessment and procedure are described in Section 7.

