7.1.1 Screening assessments (Day 1)

SARS-CoV-2 infection and vaccination history will be collected. This will include:

- dates of positive SARS-CoV-2 PCR, antigen, and/or antibody tests
- dates of symptomatic COVID-19
- date and duration of hospitalisation for COVID-19 (if relevant)
- date(s) of COVID-19 vaccine(s) administration.

Review of the main study eligibility criteria will be performed for all participants providing informed consent for the main study (baseline visit). Participants may be re-screened if they may later become eligible for participation (due to, e.g., age or interval between SARS-CoV-2 infection and screening).

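### The three-month COVID-19 exclusion is tied to the baseline visit and has no sub-study counterpart, so a participant infected after baseline can be measured in a sub-study during or soon after acute illness under baseline Long-COVID status

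*Protocol*

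**What the plan says.** - **Main-study entry.** Protocol section 5.3.2, criterion 3, excludes "COVID-19 within three months of the baseline visit". Criterion 1, for Cohort 1 only, excludes "Symptomatic SARS-CoV-2 infection at any stage prior to the baseline visit". Section 5.3 limits these criteria to the baseline visit.
- **Sub-study entry.** Section 5.4 opens: "The following additional eligibility criteria will be used to identify study participants who are eligible for random selection for any of the sub-studies". Inclusion requires "Enrolled into main study and completed baseline visit" and consent to the sub-study. The seven exclusions in section 5.4.2 cover pregnancy, smoking, biomass exposure, respiratory illness, tuberculosis and diabetes. Each applies only to the respiratory or the glucose metabolism sub-study.
- **Timing.** The Schedule of Assessments (section 1) places sub-study visits on Days 2 to 180. Section 6 says: "All study visits (including the screening/baseline visits and sub-study visits) will be completed for each participant within approximately 6 months". Section 7.2.2.4 limits the objective sleep measurements to 60 days after baseline.
- **Infection history.** Section 7.1.1, under screening on Day 1, states: "SARS-CoV-2 infection and vaccination history will be collected". The Schedule marks this item in the screening column only.
- **Case or control status.** Note 12 to the Schedule says: "Study team personnel will review each participant's baseline data and identify participants with and without Long-COVID". The exploratory objective in section 3 then compares these two groups on the sub-study measurements.

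**The concern.** By writing criterion 3, the sponsor judged that three months should separate COVID-19 from the study measurements. That separation is guaranteed for the baseline visit alone. The sub-studies hold the measurements most likely to react to a recent infection: diffusion capacity and chest CT, cardiac MRI, troponin and pro-BNP, cortisol, and leukocyte responses. The protocol's own rationale (sections 2.1 and 2.3.1) describes lung, cardiac and inflammatory effects of SARS-CoV-2.

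A recent infection in a control can move that person's values toward those of cases and shrink the contrast. In a case, acute effects can pass for Long-COVID pathology. The direction of the net bias is therefore not known in advance. Unless the infection is recorded with a date, the analysis has no reliable means of setting those participants aside.

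**Working it through.** The protocol states no sample-size, power or incidence figure to reproduce (section 9.1 says no formal calculation was made). The check is a reading of the text, a window calculation and an illustration.

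**1. Text.** Criterion 3 does not say whether it looks before or after baseline. As an entry criterion reviewed at screening, it cannot act on an infection that has not yet happened. Section 5.4 adds nothing on infection. Previous and concomitant medications are likewise collected at baseline only, and adverse events are limited to those associated with study assessments or procedures (section 8.2.1), so COVID-19 arising between visits would not be reported there. The confounders named in section 9.2.2 include prior infections but not infections after baseline.

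**2. Window.** Take three months as 90 days (assumption) and baseline as Day 1. For a sub-study visit on Day T, the part of the preceding 90 days that the baseline rule does not cover is

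u(T) = min(90, T − 1).

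| Visit day T | u(T), days | Share of 90 days |
|---|---|---|
| 30 | 29 | 32% |
| 60 | 59 | 66% |
| 91 or later | 90 | 100% |

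The window from Day 2 to Day 180 has 179 days. On 90 of them (Days 91 to 180), which is 50%, the baseline rule gives no protection. With visits spread evenly, the mean of u(T) is 12,105 / 179 = 67.6 days.

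**3. Illustration of size.** Inputs:
- Up to 30 participants per cohort in four cohorts, so 4 × 30 = 120 per sub-study (sections 6 and 7.2).
- Assumed 180-day incidence I of 5%, 10% or 20%, constant hazard, and visits spread evenly over the window. The protocol supplies none of these.

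h = −ln(1 − I) / 180

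p = mean over T = 2, …, 180 of [1 − exp(−h × u(T))]

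Expected number = 120 × p; P(at least one) = 1 − (1 − p)^120

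| I | h per day | p | Expected of 120 | P(at least one) |
|---|---|---|---|---|
| 5% | 0.000285 | 0.0191 | 2.3 | 0.90 |
| 10% | 0.000585 | 0.0387 | 4.6 | 0.99 |
| 20% | 0.001240 | 0.0798 | 9.6 | >0.99 |

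Per cohort of 30 this is about 0.6, 1.2 or 2.4 participants.

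For the sleep sub-study, the same calculation with visits spread over Days 2 to 60 gives p = 0.0085, 0.0174 and 0.0363, or 1.0, 2.1 and 4.4 of 120.

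**The case against.** **The separate sub-study plans may contain a check.** Sections 7.2.2.1 to 7.2.2.6 each refer to such a plan, and none is shown. An infection question on the visit day could be there. This stands as a limit on what can be said about data collection. It does not remove the eligibility gap: section 5.4 presents its list as the criteria for all sub-studies and refers to a plan only to define a previous smoker.

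**Some infections would come to light anyway.** A reader might infer that later infections go wholly unrecorded and can never be removed. The protocol does not support that. The cardiac sub-study includes a clinical history (section 7.2.2.2). The psychiatric and neuroendocrine sub-study has questionnaires on the impact of COVID-19, diaries and a semi-structured interview (section 7.2.2.3). None is a dated infection record and no rule is attached to any of them, so capture is possible but not systematic.

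**Cohort 1 labels remain correct.** A reader might infer that a symptomatic infection after baseline makes a Cohort 1 member misclassified. Cohorts are defined by the earlier, index infection (sections 5.1 and 5.3.1). A later infection is a new covariate and does not make the label wrong.

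**The numbers could be small.** This is fair. The text permits such measurements but does not show that they occur. Large counts also need high incidence: for 20% of participants (24 of 120) to be affected, about 45% would have to be infected within 180 days under the model above.

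**Exploratory analyses belong to the SAP.** Section 9.2.4 says so, and the absence of a sensitivity analysis from the protocol is no fault. But the SAP can use only data that the schedule collects, and eligibility is fixed in the protocol.

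**Conclusion.** The point holds in a limited form. As written, section 5.4 admits recently infected cases and controls to organ measurements that are compared by baseline Long-COVID status. From Day 91 the sponsor's own three-month safeguard has no effect on those measurements. Dated infection history is not scheduled after screening, so such infections are not systematically captured.

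It might be inferred that the main results are compromised. They are not: the primary and secondary endpoints are collected at baseline, where the exclusion applies. Only the exploratory sub-study comparisons are exposed, and the sleep sub-study less than the others.

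The window result rests only on taking three months as 90 days. The counts of 2.3, 4.6 and 9.6 per 120 also rest on an assumed incidence, a constant hazard and evenly spread visits, and should be read as illustration. The change is worth making because it is cheap and applies a standard the protocol already holds, but it is not critical to the study.

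**What to change.** 1. **Record it.** Repeat the existing SARS-CoV-2 infection and vaccination history at each sub-study visit, and mark it in the sub-study column of the Schedule of Assessments.
2. **Carry the interval over.** Add to section 5.4.2, for all sub-studies, the protocol's own three-month COVID-19 exclusion, anchored to the sub-study visit.
3. **Say what follows.** Defer the visit where the sub-study window allows. Otherwise do not enrol the participant in that sub-study, and select another eligible participant of the same cohort and Long-COVID status where possible. Note 12 now provides random replacement only for those who decline an invitation, so extend it to this case. State that this is not a withdrawal, because section 4.4 says withdrawn participants are not replaced.
4. **Analyse it.** Flag infections after baseline and, in the SAP, repeat the exploratory comparisons without those participants.

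**Cost.** One eligibility line, one existing form repeated, an extended note and one sensitivity analysis. A few visits would be deferred and a few sub-study places refilled or lost. The loss falls mainly on the sleep sub-study, where a three-month deferral cannot fit the 60-day window. In the other sub-studies, deferral after an infection later than about Day 90 would not fit the Day 180 limit either. Replacements must also respect each sub-study's ratio of participants with and without Long-COVID and, where possible, the age and gender matching in section 7.2.

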5.4.2 Exclusion criteria

1. Pregnant women **[Respiratory sub-study only]**.
2. Current or previous smokers **[Respiratory sub-study only]**; refer to Respiratory Sub-Study Plan for definition of “previous”.
3. A well-characterised history of household exposure to biomass fuel used in the dwelling for heating and/or cooking, which preceded the acute COVID-19 illness **[Respiratory sub-study only]**.
4. A well-characterised underlying comorbid respiratory illness being treated on a continuous basis, which preceded the acute COVID-19 illness **[Respiratory sub-study only]**.
5. A well-characterised history of having had tuberculosis, appropriately diagnosed and treated, prior to the acute COVID-19 illness **[Respiratory sub-study only]**.
6. A history of diabetes and/or use of treatment for diabetes mellitus (Type 1 or 2) prior to COVID-19 or asymptomatic SARS-CoV-2 infection **[Glucose metabolism sub-study only]**.
7. Current, known diabetic or on treatment for diabetes mellitus (Type 1 or 2) **[Glucose metabolism sub-study only]**.

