5.3.1 Inclusion criteria

1. Able and willing to provide written or electronic informed consent for the baseline visit prior to any study-specific assessment or procedure.
2. Age at least 18 years at the time of signing the informed consent form.
3. Previous asymptomatic SARS-CoV-2 infection, confirmed through a documented positive PCR, antigen, or antibody test, at least six months prior to the baseline visit **[Cohort 1 only]** or, previous symptomatic SARS-CoV-2 infection for which hospitalisation was not required, confirmed through a documented positive PCR or antigen test at the time, at least six months prior to the baseline visit **[Cohort 2 only]** or, previous hospitalisation for management and treatment of COVID-19 confirmed through a documented positive PCR or antigen test at the time, at least six months prior to the baseline visit **[Cohort 3 only]** or, previous asymptomatic or symptomatic SARS-CoV-2 infection, confirmed through a documented positive PCR, antigen, or antibody test, at least six months prior to the baseline visit and received a COVID-19 vaccine in a non-placebo arm of a COVID-19 vaccine study during 2020 **[Cohort 4 only]**.
4. Willing to consent to verification of vaccination status on the national Electronic Vaccination Data System (EVDS).
5. Access to a reliable telephone or other device permitting information transfer.

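### Respiratory sub-study exclusions 3 to 5 are tied to an acute COVID-19 illness that Cohort 1 and asymptomatic Cohort 4 participants never had, so as written the cohorts are screened unequally

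*Protocol*

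**What the plan says.** Section 5.4.2 of the protocol lists the sub-study exclusions; the synopsis has the same wording. Three items for the respiratory sub-study carry a time anchor, which in items 3 and 4 reads "which preceded the acute COVID-19 illness":

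- Item 3: "A well-characterised history of household exposure to biomass fuel used in the dwelling for heating and/or cooking, which preceded the acute COVID-19 illness".
- Item 4: "A well-characterised underlying comorbid respiratory illness being treated on a continuous basis, which preceded the acute COVID-19 illness".
- Item 5: "A well-characterised history of having had tuberculosis, appropriately diagnosed and treated, prior to the acute COVID-19 illness".

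Item 2, also respiratory, has no anchor: "Current or previous smokers". Item 6, for the glucose metabolism sub-study, has a wider one: "prior to COVID-19 or asymptomatic SARS-CoV-2 infection". Section 7.2.2.6 repeats that wider form.

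Cohort 1 enters under Section 5.3.1 with "Previous asymptomatic SARS-CoV-2 infection, confirmed through a documented positive PCR, antigen, or antibody test, at least six months prior to the baseline visit". Section 5.3.2 then removes anyone in that cohort with "Symptomatic SARS-CoV-2 infection at any stage prior to the baseline visit". Cohort 4 may be entered after either an asymptomatic or a symptomatic infection (Sections 5.1 and 5.3.1). Section 7.2 allows as many as 30 participants per cohort in each sub-study.

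**The concern.** An exclusion that depends on something having come before an illness cannot take effect in a person who had no such illness. Read as written, items 3 to 5 cannot exclude anyone in Cohort 1 or any asymptomatic member of Cohort 4.

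The respiratory sub-study measures high-resolution CT, spirometry and DLCO (Section 7.2.2.1), and items 3 to 5 evidently aim to remove earlier causes of abnormal results. If they work in some cohorts only, three things follow:

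- Respiratory findings are less comparable across the cohorts, which Section 4.1 says will be compared.
- Cohort 4 becomes a mixture of screened and unscreened people.
- In unscreened participants, old lung damage may pass for a Long-COVID finding. Section 2.2 describes Long-COVID as a diagnosis of exclusion, so the risk is a real one.

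**Working it through.** The protocol gives no figure to reproduce, so the main check sets the passages side by side.

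**Step 1. Does the protocol treat asymptomatic infection as COVID-19 illness?** Item 6 names the two as alternatives; the second would be redundant if the first included it. Section 7.1.2.2 collects COVID-19 history only from participants with earlier symptomatic infection. The word illness in items 3 to 5 is narrower again. The text therefore favours the reading that asymptomatic infection is not covered.

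**Step 2. Who has the anchor?**

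| Group | Acute COVID-19 illness? | Items 3 to 5 can exclude? |
|---|---|---|
| Cohort 1 | No, by inclusion and exclusion criteria | No |
| Cohort 2 | Yes, symptomatic outpatients | Yes |
| Cohort 3 | Yes, hospitalised | Yes |
| Cohort 4, symptomatic | Yes | Yes |
| Cohort 4, asymptomatic | No | No |

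Item 1 (pregnancy) and item 2 (smoking) have no anchor and apply to all five groups.

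**Step 3. How many people might this involve?** The protocol gives no prevalence for the items 3 to 5 conditions. Let p be the assumed share of otherwise eligible participants with any of them, and let n = 30, the maximum per cohort from Section 7.2.

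- Expected number in Cohort 1: 30 × p.
- Chance of at least one: 1 − (1 − p)^30.
- Expected number in Cohort 4: 30 × p × f, where f is the assumed asymptomatic share (25% to 75%; also not in the protocol).

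| Assumed p | Cohort 1 expected | Chance of at least one | Cohort 4 expected (f = 25% to 75%) |
|---|---|---|---|
| 5% | 1.5 | 78.5% | 0.38 to 1.12 |
| 10% | 3 | 95.8% | 0.75 to 2.25 |
| 20% | 6 | 99.9% | 1.5 to 4.5 |
| 30% | 9 | about 100% | 2.25 to 6.75 |

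In Cohorts 2 and 3 the expected number is 0 if the exclusions are fully applied.

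**Step 4. Which comparisons are touched?** The exploratory objective (Section 3) sets participants with Long-COVID against controls from the same cohorts. Within Cohort 1 both groups are unscreened, so the wording creates no difference in screening between them. A pre-existing condition could still cause both the symptom that leads to a Long-COVID label and the abnormal test. Within Cohort 4, screening depends on whether the infection was symptomatic; if that is related to Long-COVID status, the two groups are screened unequally. Between cohorts, the imbalance is direct.

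**The case against.** The best reply is that nobody would apply the text so literally. The protocol uses COVID-19 loosely in places: it adds the word symptomatic to it in Sections 5.1 and 7.1.1, which would be unnecessary if the term always implied symptoms. Staff may well take the anchor to mean the index infection, and item 6 suggests the drafters intended that. The Respiratory Sub-Study Plan, which is not at hand, may define it. Medical history is also taken from everyone (Section 7.1.2.2), so earlier tuberculosis or chronic respiratory illness could be identified and described at analysis.

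Part of this stands. Nothing shows that the criteria will be applied literally. But item 2 refers to the sub-study plan for a definition and items 3 to 5 do not, and an eligibility rule that relies on staff ignoring its wording may be applied differently from one person to the next. Biomass exposure is not named among the baseline data in Section 7.1.2.1, so item 3 may not be recoverable later.

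A reader might also infer more than the text supports:

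- **That only one cohort is affected.** Asymptomatic Cohort 4 members lack the anchor too.
- **That lung disease in general is let in.** Item 3 is an exposure, only items 4 and 5 are diseases, and smokers are excluded everywhere.
- **That a severity gradient sought by the sub-study is flattened.** The stated exploratory contrast is with controls from the same cohorts; comparison across cohorts appears only as general design language in Section 4.1.
- **That the excess of abnormal CT scans can be quantified.** The protocol gives no CT abnormality rate for people with or without these histories, so any such figure is assumption. With 30 per cohort it would also be hard to see: the exact 95% interval around 3 of 30 runs from roughly 2% to 27%.

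**Conclusion.** The point holds as an inconsistency in the eligibility text, within one list of exclusions, that leads to unequal screening if the text is followed. It leaves all of Cohort 1 and the asymptomatic part of Cohort 4 unscreened for items 3 to 5.

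Its effect on the respiratory results is unknown. The Step 3 counts rest on assumed prevalences and on full recruitment of 30 per cohort; they show only that at least one affected Cohort 1 participant is likely even at the low end. The sub-study is exploratory and no sample size was calculated (Section 9.1), so no powered conclusion is at risk. What suffers is the comparability of respiratory findings between cohorts and within Cohort 4, and the attribution of abnormal findings to Long-COVID among unscreened participants.

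**What to change.** In items 3, 4 and 5, in Section 5.4.2 and in the synopsis, replace the present anchor with the item 6 wording, "prior to COVID-19 or asymptomatic SARS-CoV-2 infection", so that one anchor covers every cohort. Bring the Respiratory Sub-Study Plan into line if it says otherwise.

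Add a sentence on dating. Cohort 1 and Cohort 4 participants may qualify by antibody test alone, and a positive antibody result does not show when infection occurred. For them, the positive-test date should be the latest possible date of infection, not the infection date itself. A condition that began after that date did not precede the infection. For one that began before it, the order may remain uncertain and should be recorded as such.

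The cost is one phrase in three criteria, repeated in the synopsis, plus the dating sentence, submitted as a protocol amendment. Positive-test dates are already collected at screening (Section 7.1.1), so the reference date needs no new data. Applying the items to all cohorts will somewhat reduce the eligible pool in Cohorts 1 and 4.
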